3.0 Study Endpoints/Events/Outcomes

- 3.1 Primary Endpoint/Event/Outcome: The primary outcome is magnitude of brain excitability as measured by motor evoked potentials from TMS. The primary behavioral outcome is time to complete a novel movement task.
- 3.2 Secondary Endpoint(s)/Event(s)/Outcome(s): The secondary neurophysiological outcomes are interhemispheric inhibition as measured by ipsilateral silent period (iSP) and paired pulse (PP) TMS (see 5.2 Study Procedures). The secondary behavioral outcomes are the Box and Blocks Test and Grip Strength. Safety and tolerability of the study, as measured through our participant-report of symptoms questionnaires, are also secondary outcomes.

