5.0 Procedures Involved

5.1 Study Design: This is a randomized, sham-controlled, double-blinded study. The intervention consists of a single, 20 minute session of tDCS paired with motor training (see Figure 2). Participants will be randomized to either real or sham tDCS. The participants and the members of the research team involved in assessments and testing will be blinded to intervention group (real or sham tDCS), but the other research staff/PI/Co-Is will be unblinded.

5.2 Study Procedures:

Pre-study

[figure not shown]

Figure 2. Pre-study timeline and study design.

Participant Screening and Enrollment

Participants will be initially screened for inclusion and exclusion criteria during a phone interview (Appendix A). Initial consent will be obtained over the phone to allow the caregiver to disclose protected health information (PHI) about his/her child. If the family is interested following this phone screen, we will obtain HIPAA consent to perform a medical record review (Appendix B and C). A review is then completed by the study medical director for review of inclusion/exclusion by history and MRI/CT radiographic reports of the brain (Appendix D). Eligibility will be verified by the principal investigator after this review. Eligibility is then discussed with the legal guardian and a formal schedule is established. A pre-study letter will then be sent (Appendix E). Informed consent/assent will be completed before on the day of the MRI acquisition.

The research team will utilize the CMRR Center's screening tools and adhere to the screening SOP during enrollment of all research participants in this protocol. The CMRR Center's screening tools and SOP are IRB approved under the CMRR Center Grant (HSC# 1406M51205) and information regarding screening procedures is publically available on the CMRR website.

Randomization

Participants will be randomly assigned to receive real or sham tDCS. Children with presence of a lesioned hemisphere MEP response may receive 1) ipsilesional anodal; 2) contralesional cathodal tDCS or 3) sham tDCS. Children without a lesioned hemisphere MEP may receive 1) contralesional anodal or 2) sham tDCS. Participants and their families will be blinded to group assignment. Participants will be unblinded after completing the study.

Magnetic Resonance Imaging (MRI) Acquisition

Location: Center for Magnetic Resonance Research (CMRR)

Time: 1 hour (including preparatory time)

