After the first 2 minutes of stimulation, the participant is questioned about pain at the electrode sites. If the stimulation is painful, a small amount of additional saline (2-4 mL) is added to the sponge, taking care to avoid wetting adjacent hair and thereby increasing the electrode area, and the tightness and placement of the band are checked. If pain persists, the stimulation intensity is decreased, and symptoms re-assessed. If pain still persists, stimulation is stopped and the electrode sites are checked. This procedure is repeated twice (every 5 minutes during tDCS) with saline solution (2-4 mL) added as needed.

Participants will receive a total of 20 minutes of active or sham tDCS. During stimulation, participants will practice the novel reaching task described above at a comfortable pace. No conversations between participant and researchers or caregivers will be allowed, except those that pertain to safety.

Post-intervention Assessments

Immediately following the intervention, TMS and Behavioral assessments will be performed at 0, 15, 30, and 60 minutes following the intervention (see Figure 2).

Other Procedures

Computational Modeling

Computational modeling of electric fields produced by tDCS will be performed using SimNIBS (Simulation of Non-invasive Brain Stimulation). Using T1-anatomical images, individual skull and brain anatomy will be reconstructed, and electric fields computed using a finite element method. The primary outcome is the estimated peak electric field strength for the M1-SO montage.

Safety Monitoring

We will use questionnaires (Appendix F) to document symptoms associated with non-invasive brain stimulation before and after the intervention and testing session. This tool asks participants about the presence and severity of symptoms such as tingling, itchiness, and headache. We will also measure heart rate and blood pressure before and after the procedures.

Follow-Up: A member of the research team will contact each participant and their caregivers within one week of completing the study to check for any adverse events. There is no long-term follow-up data collection planned.

- 5.3 Study Duration: Each participant will complete the study in either one day (MRI and intervention, four hours total) or on two separate days (one hour MRI, and three hours intervention). If done on two days, the MRI and intervention will be separated by no longer than a two week (14 day) period.

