15.0 Data Management

- 15.1 **Data Analysis Plan:** Baseline and demographic information will be summarized by descriptive statistics for continuous variables, and the number and percentage of participants in each category for categorical variables. The primary analysis will compare changes in behavioral and neurophysiologic measures between the two intervention groups (real and sham tDCS). When possible, we will use repeated measures ANOVA to account for differences between groups. If measures are non-normally distributed, we will use Wilcoxon signed-ranks tests. We will use correlation analysis to compare modeled peak electric field strength with changes in behavioral and neurophysiologic outcomes.

Summary of power analysis with alpha of 0.0125 and N per group of 8			
Correlation	MEP		
	Δ	SD	Power
0.3	0.75	0.5	0.71
0.4	0.75	0.5	0.75
0.5	0.75	0.5	0.81
0.6	0.75	0.5	0.87
0.7	0.75	0.5	0.94

- 15.2 **Power Analysis:** With the data and literature available, we completed power calculations for the primary neurophysiological outcome, MEP, and the behavioral clinical outcome, the Assisting Hand Assessment (AHA) scaled score (Table 2). These were based on the difference between the pre- and post-test measurements

adjusting for baseline values, similar to ANCOVA analyses, for added precision. These calculations used the sample size formula for normally distributed statistics with a Bonferroni corrected type I error level of 0.0125 for the four potential primary comparisons between the: 1) Anodal Ipsilesional tDCS group versus Sham_c tDCS, 2) Cathodal Contralesional tDCS versus Sham_c tDCS, 3) Anodal Ipsilesional tDCS group versus Cathodal Contralesional tDCS, and 4) Anodal Contralesional tDCS versus Sham_i tDCS to maintain an overall type I error level of 0.05. Power was computed for 8 participants per treatment group across a range of possible values for the correlation between pre- and post-treatment measurements. These were computed for a change in the MEP of 0.75 mV. The mean change and standard deviation of the MEP in the study population was based on the tDCS/CIMT study. The correlation between pre- and post-treatment MEP in the tDCS/CIMT study was approximately 0.5. Based on these estimates, we will have 81% power to detect a change in the MEP of 0.75 mV, which translates into a large effect size (Cohen's $d = 1.5$).

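### Section 15.1's only fallback for non-normal measures is a paired test, so task time or a secondary measure judged non-normal would have no planned real-versus-sham test

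*Combined protocol and SAP*

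**What the plan says.** Section 5.1 describes parallel groups: "Participants will be randomized to either real or sham tDCS". There is one exposure per child: "The intervention consists of a single, 20 minute session of tDCS paired with motor training". No crossover or matching is described. Under Randomization in 5.2, children with a lesioned-hemisphere MEP may receive ipsilesional anodal, contralesional cathodal or sham tDCS; children without one may receive contralesional anodal or sham.

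Section 15.1 sets a between-group aim: "The primary analysis will compare changes in behavioral and neurophysiologic measures between the two intervention groups (real and sham tDCS"). The main method is conditional: "When possible, we will use repeated measures ANOVA to account for differences between groups". One alternative follows: "If measures are non-normally distributed, we will use Wilcoxon signed-ranks tests".

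Section 3.1 makes task time a headline outcome: "The primary behavioral outcome is time to complete a novel movement task". Section 3.2 lists iSP and paired-pulse TMS as secondary neurophysiological outcomes and adds: "The secondary behavioral outcomes are the Box and Blocks Test and Grip Strength".

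Section 15.3 gives a separate comparison of each active group with sham, adjusted for baseline and using robust variance, but it names only the MEP.

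**The concern.** The signed-rank test needs one sample or paired observations. The only pairing here is pre with post in the same child, so the test asks whether a group changed. It does not ask whether real changed more than sham. If the fallback is followed literally for an outcome, the randomised sham comparison is not tested for that outcome.

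This matters most for task time, because the task is rehearsed in every arm: "During stimulation, participants will practice the novel reaching task described above at a comfortable pace". Children on sham can improve through practice. Two separate within-group tests could give a significant result on real and a non-significant one on sham although both groups improved equally. A true difference between the groups could also go untested.

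**Working it through.** **1. Which outcomes lack a between-group test if judged non-normal**

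| Outcome | Between-group efficacy analysis outside 15.1 |
|---|---|
| MEP | Yes: 15.3, baseline-adjusted, against sham |
| Task time (primary behavioral) | None |
| iSP, paired-pulse | None |
| Box and Blocks, grip | None |
| Safety and tolerability | Mainly descriptive; no test needed |

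Section 17.2 compares real with sham on the reaching task, but as an interim safety rule with a 2 SD threshold, not as an efficacy test. No section names a rank-sum or other between-group rank test. The conclusion rests on this comparison of sections alone.

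**2. Illustration of what within-group testing can do**

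The documents give no practice effect, no sidedness and no alpha for task time. Assumed: no tDCS effect, normal changes, the same practice shift k (in SDs of change) in every arm, and an exact two-sided signed-rank test per group. The group size of 8 is from 15.2; the level of 0.0125 is set in 15.2 and 15.3 but not for task time.

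For n = 8 the smallest two-sided p-value is 2/2^8 = 0.0078 and the next is 0.0156. Significance at 0.0125 therefore needs all eight changes in one direction:

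q = Φ(k)^8 + Φ(−k)^8

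The chance that real is significant and sham is not is q(1 − q).

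| k | q | q(1 − q), 8 v 8 at 0.0125 | 8 v 8 at 0.05 (simulated) |
|---|---|---|---|
| 0.5 | 0.052 | 5.0% | 15.5% |
| 1 | 0.251 | 18.8% | 24% |
| 1.5 | 0.575 | 24.4% | 7% |
| 2 | 0.832 | 14.0% | 1% |

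If the 40 children with UCP in 10.1 form five arms of 8 and are pooled as 24 real and 16 sham, the chances at the same shifts are 30%, 17%, under 1% and 0% at 0.0125, and 36%, 5%, 0% and 0% at 0.05. They fall at large shifts because both groups become significant. An exact rank-sum test on change, 8 v 8, rejects in 2P(U ≤ 8) = 1.04% at nominal 1.25%, whatever the shared shift.

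**3. What the replacement test costs if the data are normal**

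The MEP inputs of 15.2 serve only as a scale: difference 0.75 mV, SD 0.5, correlation 0.5, 8 per group, alpha 0.0125. The plan states 81% power. With residual SD 0.5 × √(1 − 0.5²) = 0.433, a one-sided baseline-adjusted t calculation (13 df) gives 81.1%, a two-sided normal one 83.3% and a two-sided t 70.7%. The present point does not depend on which was used.

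The SD of unadjusted change is 0.5 × √(2 × (1 − 0.5)) = 0.5, so d = 0.75/0.5 = 1.5. Two-sided power is then:

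- t test on change (14 df), size 0.0125: 56.7%
- t test on change, size 0.0104: 53.5%
- exact rank-sum on change, actual size 0.0104: about 51%
- baseline-adjusted t test (13 df), size 0.0125: 70.7%

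Of the roughly 6 points between 57% and 51%, about 3 (56.7 − 53.5) come from the discreteness of the exact test and about 3 (53.5 − 51) from ranking. With heavy-tailed t(3) changes of the same SD, the rank-sum test has 72% and the t test 71%.

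**The case against.** The strongest reply is that this is a one-word slip. The aim stated just before it in 15.1 is between groups, as are 15.3 and the interim rule in 17.2, so a sensible analyst would run a rank-sum test. That is plausible and keeps the grade low. It does not remove the point: no between-group rank test is written down, and substituting one after seeing the data would be an unplanned choice.

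The gap is also conditional. It needs a measure to be judged non-normal and the sentence to be applied as written. The powered outcome, MEP, is largely outside it. Section 14.1 does not expect movement benefit in children with UCP. All this stands, but task time remains the primary behavioral outcome and motor performance is part of Aim 2.

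A reader might infer that the plan intends to claim a tDCS effect from a significant real group and a non-significant sham group, or that its false-positive risk is as high as 36%. The documents support neither. No section plans that inference, and the percentages rest on assumed practice shifts and on normal changes, which is not the case that triggers the fallback.

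**Conclusion.** The point holds as a defect in the wording of 15.1. The named fallback cannot answer the question set in the same paragraph, and nothing elsewhere supplies a between-group efficacy test for task time, iSP, paired-pulse, Box and Blocks or grip if any of these is judged non-normal. This follows from the text and needs no simulation; the illustrative percentages carry no weight in the grading.

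It would be too strong to say that the trial has no valid between-group analysis. Repeated measures ANOVA remains the first choice where it can be used, and 15.3 largely covers MEP. Nor do the documents show that task time will be non-normal; they give no distribution for it. Severity: should be fixed, at the low end, because the error is definite and reaches a primary outcome but is conditional and cheap to correct.

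**What to change.** In 15.1, replace the signed-rank test with a between-group rank test of change, such as an exact Wilcoxon rank-sum test or a permutation test of baseline-adjusted change. State two further things:

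- **Comparison.** Apply the test to the within-stratum comparisons listed in 15.2. If real and sham are pooled, stratify by lesioned-hemisphere MEP status, because the available arms differ by that status.
- **Time point.** Use the same post time as 15.3's primary pre-to-post change, with 30 minutes as secondary. Write that time out, since 5.2 schedules assessments at 0, 15, 30 and 60 minutes.

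Do not add a statement that 15.3 governs MEP whatever its distribution. The robust variance there is unspecified, and the choice matters in arms of 8. In a simulation of baseline-adjusted regression with no effect and normal data, at nominal 1.25%, rejection ran from 4.6% (uncorrected sandwich, normal critical values) to 0.8% (HC3 with t critical values).

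The cost is a few sentences, with no new data, visits or participants. The statistical cost is the loss of about 6 points of power against a t test on change if data are in fact normal. A permutation test of baseline-adjusted change would keep the precision that baseline adjustment brings.

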15.3 Statistical Analysis: Descriptive analyses of baseline characteristics and outcomes will include means and standard deviations for continuous variables and frequencies for categorical variables. Compliance and tolerance of the intervention will also be evaluated. Safety analyses will be primarily descriptive reporting the number and percentage of any adverse events and will be evaluated and monitored throughout the trial.

This analysis will be conducted based on the intent-to-treat principle to compare the mean neurophysiologic change measured using the MEP from pre- to post- intervention between each tDCS stimulation dose group and sham tDCS adjusted for baseline neurophysiologic measures. Confidence intervals and p-values will be based on robust variance estimation. Statistical significance will be considered as $p < 0.0125$. Supportive analyses may be conducted with consideration of adjustment for residual imbalances between treatment groups after randomization (e.g., gender). The primary analysis will evaluate the change between pre- and post- measurements. A secondary analysis will evaluate the change between pre- and 30 minutes post.

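### The primary MEP contrasts differ across 15.1, 15.2 and 15.3; one list should be fixed and tested with Holm's procedure, or at least with a threshold that matches the list

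*Combined protocol and SAP*

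**What the plan says.** Section 5.2 (Randomization) defines the arms. Children with a lesioned-hemisphere MEP "may receive 1) ipsilesional anodal; 2) contralesional cathodal tDCS or 3) sham tDCS"; children without one receive contralesional anodal or sham. That is three active arms and a sham arm in each stratum.

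The analysis sections then describe the primary comparison in three ways:

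- **15.1** compares changes "between the two intervention groups (real and sham tDCS"): one contrast.
- **15.2** uses a "Bonferroni corrected type I error level of 0.0125 for the four potential primary comparisons", in order "to maintain an overall type I error level of 0.05". Three of the four are active versus sham. The other is "3) Anodal Ipsilesional tDCS group versus Cathodal Contralesional tDCS".
- **15.3** compares mean MEP change "between each tDCS stimulation dose group and sham tDCS", adjusted for baseline, and keeps 0.0125 as the significance threshold. It lists no contrasts, and names neither the anodal-versus-cathodal comparison nor a step-down rule or test order.

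**The concern.** The family of primary tests decides which results are confirmatory and what threshold each must meet. Here it could have one, three or four members. If 15.2 governs, the anodal-versus-cathodal contrast has alpha but no analysis in 15.3. If 15.3 governs, three tests are held to a threshold derived for four. If 15.1 governs, no correction across arms is needed. An analyst could settle this after seeing the data.

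The second issue is efficiency. The UCP maximum of 40 in 10.1 equals five arms of 8, so extra children cannot supply power. A fixed 0.0125 for every contrast gives up power that a step-down procedure with the same 5% familywise error would keep in many scenarios.

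**Working it through.** **Inputs.** From 15.2 and its table: 8 per group, difference 0.75 mV, SD 0.5 mV, pre-post correlation 0.5, overall alpha 0.05, stated power 81%. From 5.2: the arms. Assumed, because not stated: two-sided tests, equal groups and no dropout.

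**Thresholds.** 0.05/4 = 0.0125, as in the plan. 0.05/3 = 0.0167.

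**The plan's own power.** Baseline-adjusted SD = 0.5 × √(1 − 0.5²) = 0.433. Standard error of a difference = 0.433 × √(2/8) = 0.2165. Standardised difference = 0.75/0.2165 = 3.464.

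- At 0.0125: Φ(3.464 − 2.498) = 83.3%, against the stated 81%. A two-sided normal formula does not reproduce the plan's figure exactly; a one-sided t with 13 df gives 81.1%. Section 15.2 does not state sidedness.
- At 0.0167: Φ(3.464 − 2.394) = 85.8%.
- By two-sided t with 13 df: about 71% at 0.0125 and 75% at 0.0167.

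**Familywise error if 15.3 governs.** Three tests at 0.0125 cannot exceed 3 × 0.0125 = 3.75%. Simulation under the global null, with the two MEP-present contrasts sharing one sham arm, gives 3.6%. For four contrasts at 0.0125 it gives 4.6%.

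**Holm against the fixed threshold.** Holm orders the p-values and compares them in turn with 0.05/4, 0.05/3, 0.05/2 and 0.05, stopping at the first failure. Simulation: 400,000 trials, five arms of 8, two-sided z, each working arm shifted by 0.75 mV. Entries are power for a working active arm against its sham:

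| Which arms work | Fixed 0.0125 | Holm, four contrasts | Holm, three sham contrasts |
|---|---|---|---|
| All, cathodal opposite to anodal | 83% | 92–93% | 92–93% |
| All, same direction | 83% | 88% | 92% |
| Both anodal arms, cathodal null | 83% | 88% | 89% |
| Ipsilesional anodal only | 83% | 85% | 86% |
| Contralesional anodal only | 83% | 83% | 86% |

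The first row is the most favourable to four-contrast Holm because anodal versus cathodal then differs by 2 × 0.75 = 1.5 mV. It is rejected almost always, which relaxes the threshold for the others.

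**Scaled to the plan's 81%.** If one contrast is set to have 81% power at 0.0125, four-contrast Holm gives about 91%, 86%, 83% and 81% in the first, second, fourth and fifth rows. The chance of winning all three sham contrasts rises from 51% to 77% (opposite direction) or from 57% to 69% (same direction).

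**At least one rejection.** Holm's first step over four contrasts is still 0.0125, so this chance equals Bonferroni's in every scenario.

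**The case against.** Bonferroni is prespecified, valid under any dependence and consistent with the power table, so Holm is an improvement and not the repair of an error. That stands. A reader might infer that the mismatch inflates type I error for the MEP contrasts. It does not: three or four tests at 0.0125 stay below 5%.

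A reader might also take a gain of about ten points as what Holm delivers whenever the arms work as planned. The documents do not support that. Section 2.1 describes polarity-specific effects, which suggests opposite signs. It also says that inhibiting the non-lesioned side may help the lesioned side, which could move lesioned-side MEPs the same way in both arms. Section 15.3 does not say which hemisphere's MEP is primary. The gain runs from nil to about ten points.

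The three-contrast count is inferred from 5.2, and 15.3 may carry the four contrasts over in loose wording. That is possible, but an analyst cannot tell, and 15.1 gives yet another version.

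Section 3.1 also names a primary behavioural outcome. If it shares the 5%, the family is larger and 0.0125 is not too strict. Section 15.2 divides alpha over the listed between-arm contrasts only, so the efficiency statement here is limited to the MEP contrasts.

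Finally, 15.3 commits to confidence intervals, and with 8 per arm these matter. Bonferroni intervals match Bonferroni tests; Holm has no equally simple match. That is a real but manageable cost.

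**Conclusion.** The inconsistency stands on the text alone: 15.1, 15.2 and 15.3 imply one, four and three primary MEP contrasts, and anodal versus cathodal is primary in one section and absent from another. The consequence is an undefined family and lost efficiency, not a false-positive problem. If 15.3 governs, about 3.6% of the permitted 5% is used.

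Replacing the fixed threshold with Holm never loses a rejection. Over four contrasts it takes power for a working arm against sham from 83% to between 83% and 93%, depending on which arms work and in which direction; over the three sham contrasts the range is about 86% to 93%. These figures rest on two-sided normal theory, correlation 0.5, full groups of 8 and no dropout. They start from 83%, not the plan's 81%, and small-sample t power is lower for both procedures. The point should be fixed before analysis but does not invalidate the design.

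**What to change.** 1. List one set of primary MEP contrasts, in identical words, in 15.1, 15.2 and 15.3, and say whether anodal ipsilesional versus cathodal contralesional belongs to it. If it does, add it to the analysis in 15.3; if not, label it secondary in 15.2.
2. Test that set with Holm's step-down procedure at overall 0.05, in place of 0.0125 for each contrast. At minimum, match the threshold to the list: 0.0125 for four, 0.0167 for three.
3. Report Bonferroni intervals alongside (98.75% for four contrasts, 98.33% for three), and state that they may not agree exactly with the step-down decisions.
4. State sidedness and the exact power formula in 15.2, and recompute the table if the threshold changes.

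The cost is wording and a short recalculation, with no change to arms, sample size or data collection. The one statistical downside is the interval mismatch in item 3.

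### Section 15.3 bases the primary MEP tests on robust variance at about 8 children per arm but names no small-sample correction or reference distribution, so the actual level of the 0.0125 test is left open

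*Combined protocol and SAP*

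**What the plan says.** Section 15.3 compares mean MEP change from before to after the intervention "between each tDCS stimulation dose group and sham tDCS adjusted for baseline neurophysiologic measures", and judges significance at p < 0.0125. On the method of inference it says only "Confidence intervals and p-values will be based on robust variance estimation". Nothing in the document names the type of sandwich estimator, a finite-sample correction, a t or normal reference, or degrees of freedom.

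Section 15.2 sets the size of the problem: "Power was computed for 8 participants per treatment group across a range of possible values for the correlation". The level 0.0125 is 0.05/4, chosen "to maintain an overall type I error level of 0.05". On power it states "These calculations used the sample size formula for normally distributed statistics" and concludes that "we will have 81% power to detect a change in the MEP of 0.75 mV".

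Section 15.1 does not fill the gap. It says "When possible, we will use repeated measures ANOVA to account for differences between groups" and "If measures are non-normally distributed, we will use Wilcoxon signed-ranks tests", neither of which specifies the robust method in 15.3. Which of the two sections governs is a separate point.

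**The concern.** The sandwich estimator is justified by large samples. A baseline-adjusted comparison of 8 v 8 children has 16 - 3 = 13 residual degrees of freedom. At that size the raw sandwich tends to understate the variance, and a normal critical value (2.498 at two-sided 0.0125) is well below the t value on 13 degrees of freedom (2.896). Several forms fit the sentence in 15.3, and they do not have the same level.

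At stake is whether 0.0125 does what 15.2 asks of it. The choice can decide whether a result crosses the threshold and, left open, it can be made after the data are seen. It also bears on power, because the stated 81% comes from a normal formula and does not carry over to a test that controls its level with 13 degrees of freedom.

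**Working it through.** **Inputs.** Level 0.0125 (15.2 and 15.3; sidedness is not stated, two-sided assumed). 8 per arm, difference 0.75 mV, SD 0.5, correlation about 0.5 (15.2). Up to 40 children with UCP (10.1), which is five groups of 8. SD 0.5 is taken as the SD at each time point.

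**1. The plan's own power figure.** The normal ANCOVA formula is power = Φ(Δ/SE - z), with SE = SD·√(1 - ρ²)·√(2/n).

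- SD 0.5, ρ = 0.5: SE = 0.5 × 0.866 × 0.5 = 0.2165; 0.75/0.2165 = 3.464; 3.464 - 2.498 = 0.966; power 0.833.
- Over ρ = 0.3 to 0.7 this gives 0.741, 0.781, 0.833, 0.895, 0.956, against the printed 0.71, 0.75, 0.81, 0.87, 0.94.
- SD 0.515 gives 0.711, 0.752, 0.807, 0.873, 0.943, which matches all five entries. It prints as 0.5, and 0.75/0.515 = 1.46 still rounds to the stated d of 1.5.

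So the formula is identified, and the small gap is consistent with rounding of the SD.

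**2. Actual level at nominal 0.0125.** Simulated null trials (120,000 or more per set-up in the main runs), normal data, 8 v 8, MEP regressed on arm and baseline, ρ = 0.5. HC0 is the raw sandwich. HC1 multiplies it by N/(N - k), here 16/13. HC2 and HC3 divide each squared residual by (1 - h) and (1 - h)², where h is the leverage. Ranges show the spread between independent runs.

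| Form | Actual level |
|---|---|
| HC3, t | 0.008 |
| HC2, Satterthwaite df | 0.012-0.013 |
| Ordinary ANCOVA, t | 0.013 |
| HC1 or HC2, t | 0.014-0.016 |
| HC0, t | 0.024-0.026 |
| Ordinary ANCOVA, normal | 0.027 |
| HC1 or HC2, normal | 0.030 |
| HC0, normal | 0.046 |

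Correlations of 0.3 and 0.7 change little (HC0 normal 0.046 and 0.049; HC3 t 0.007 and 0.009).

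**3. Where the excess comes from.** Ordinary ANCOVA goes from 0.013 to 0.027 on changing t to normal, with no sandwich involved. HC1 with a normal reference adds only 0.030 - 0.027 = 0.003 to that. The raw sandwich has its own effect: HC0 with t is already about 0.024.

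**4. Pairwise or pooled.** From HC3 with t to HC0 with a normal reference, the range is about 0.010 to 0.040 in a pooled three-arm model and 0.012 to 0.037 in a pooled five-arm model. HC1 or HC2 with t on residual degrees of freedom moves further from nominal when pooled: 0.017 (three arms) and 0.020 (five arms).

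**5. Power at 0.75 mV, SD 0.5, ρ = 0.5.**

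| Form | 8 v 8 | Pooled 3-arm | Pooled 5-arm |
|---|---|---|---|
| HC2, Satterthwaite df | 64% | 68% | 70% |
| Ordinary ANCOVA, t | 67% | 73% | 77% |
| HC3, t | 56% | 64% | 70% |

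At SD 0.515 these fall by a few points; 8 v 8 ANCOVA with t is about 64%.

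**6. Unequal variances.** With one arm's post-test SD doubled, a pooled three-arm contrast involving that arm runs at 0.027 for ordinary ANCOVA with t and 0.016 for HC2 Satterthwaite. At 8 v 8 the two are 0.015 and 0.014.

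**The case against.** The strongest reply is that nothing in the plan commits the trial to a bad form. No section names HC0, and the only normal reference is in the power formula of 15.2, not in the test of 15.3. A statistician who used HC1 or HC2 with t in a pairwise model would be at 0.014-0.016, near nominal. HC1 is itself a finite-sample correction. The rates also depend on the data: with lognormal data (sigma 0.5 and 1.0, same shape in both arms), HC0 with a normal reference falls to 0.039 and 0.029, and HC1 with t to 0.011 and 0.006. That is one family of distributions and not a general result. All of this stands, and it is why the point is one of specification.

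The power shortfall is also not caused by robust variance. It comes from using a normal formula and appears for ordinary ANCOVA with t as well. That stands too, so it is put as a separate consequence.

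Three stronger readings are tempting and are not supported.

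- A reader might infer that overall error is well above 0.05. Under HC0 with a normal reference it would be 1 - (1 - 0.1002)(1 - 0.0460) = 0.14 over the four comparisons, where 0.1002 is the chance of any rejection in the three-arm stratum. That describes a form the plan does not state.
- A reader might infer that the claimed error rate and the claimed power are incompatible. They are not in every case: the correlation is given only as approximate, and a pooled five-arm ANCOVA with t reaches 81% at a correlation of about 0.55, holding its level if variances are equal.
- A reader might infer that the power table is wrong. An SD rounded from about 0.515 reproduces it.

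**Conclusion.** The omission is real and worth correcting. At about 8 per arm, the forms compatible with 15.3 have actual levels from about 0.008 to 0.046 for a nominal 0.0125, nearly a six-fold spread. The documents do not show that the trial's error rate is inflated, because they do not say which form will be used.

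The 81% power needs restating. None of the level-controlling tests examined reaches it at correlation 0.5 and SD 0.5: they give about 56-67% at 8 v 8 and about 70-77% in a pooled five-arm model.

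These figures assume a two-sided test, normal data, equal variances unless stated, 8 children in every arm, and SD 0.5 as the SD at each time point.

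**What to change.** In 15.3, add that the baseline-adjusted MEP contrasts use robust variance in the HC2 form with Satterthwaite degrees of freedom, and that neither HC0 nor a normal reference will be used. State whether the contrasts are fitted pairwise or in one pooled model. This keeps the planned robust method.

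Ordinary ANCOVA with t on residual degrees of freedom is an alternative only if the plan is willing to assume equal variances, since it gives up the protection that robust variance is there to provide.

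In 15.2, restate the power for the chosen test: about 64% for pairwise HC2 Satterthwaite at correlation 0.5 and SD 0.5, and a few points less if the SD is nearer 0.515.

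The cost is one or two sentences and a standard calculation, with no added participants, visits or procedures. The downside is a lower stated power and slightly wider intervals, on average 1.04 times the ordinary t interval at 8 v 8.
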